10.2.3 Measurement Methods

Response assessment will be performed based on CT imaging. CT scan is the preferred mode of imaging, however, if a CT scan is contraindicated or if it is felt by the Sponsor Investigator that a PET/CT will be a better modality to assess a particular subject, a PET/CT may be used for evaluation.

10.2.4 Measurement Time Points

Subjects will undergo imaging studies at screening, and at the 12 Week visit. Imaging will be performed at Week 24 as part of routine follow-up and to assess safety and response. Subsequent imaging as part of routine follow-up will be done every 3 to 6 months.

10.3 Phase 2 - Secondary Outcome Measure – Progression free survival

The secondary outcome measure for the phase 2 portion will be progression-free survival.

10.3.1 Relevant Subset

This outcome will be measured on any individual who has received at least one intratumoral injection of SD-101 at the recommended phase 2 dose level. This will include any subjects treated during the phase 1B portion who were treated at the recommended phase 2 dose level.

10.3.2 Progression-free Survival Definition

Progression-free Survival is defined as the time elapsed between treatment initiation (Day 1) and tumor progression or death from any cause. Progression will be defined using the Lugano Classification (Section 10.2.2, Table 6). It is recommended in difficult cases to confirm PD by serial imaging. If it is felt by the Sponsor Investigator that a participant may be experiencing immune-related pseudoprogression resulting in PD, then at the discretion of the Sponsor Investigator, that participant may continue on study until the next response assessment. Participants who meet the definition for PD on two consecutive response assessments will be assessed as PD and treatment must be discontinued

10.3.3 Measurement Methods

Progression will be assessed based on CT imaging. CT scan is the preferred mode of imaging, however, if a CT scan is contraindicated or if it is felt by the Sponsor Investigator that a PET/CT will be a better modality to assess a particular subject, a PET/CT may be used for evaluation.

10.3.4 Measurement Time Points

Subjects will undergo imaging studies at screening, and at the 12 Week visit. Imaging will be performed at Week 24 as part of routine follow-up and to assess safety and response. Subsequent imaging as part of routine follow-up will be done every 3 to 6 months.

10.4 Phase 2 - Secondary Outcome Measure – Induction of tumor-specific immune responses

An additionally exploratory secondary outcome measure for the phase 2 portion will be the induction of tumor-specific immune responses.

10.4.1 Relevant Subset

This outcome will be measured on any individual who has received at least one intratumoral injection of SD-101 at the recommended phase 2 dose level. This will include any subjects treated during the phase 1B portion who were treated at the recommended phase 2 dose level. This analysis will be limited to individuals with adequate research samples collection to perform the required assays.

10.4.2 Tumor-specific Immune Response Definition

Tumor-specific immune responses will be defined as lymphocyte activity against autologous tumor over the baseline of activity against media only.

10.4.3 Measurement Methods

Tumor-specific immune responses will be assayed as in section 8.3, *Lymphocyte activity against autologous tumor*.

10.4.4 Measurement Time Points

Tumor-specific immune responses are calculated as the increase in percentage of activated T-cell subsets (CD4 or CD8) specifically in response to co-culture with autologous tumor at

post-treatment time points compared to pre-treatment time points. All post-treatment time points will be evaluated, but the primary timepoint for analysis will be from Day 37 samples.

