- Fine needle aspiration of planned treatment site (if no tissue from excisional biopsy is available for correlative studies). If additional sites of disease are safely accessible via fine needle aspiration, these may be biopsied as well.
- An excisional biopsy may be performed to confirm that the tumor has not transformed to a more aggressive form (optional). Tissue/cells not required for clinical diagnostic assessment may be collected and stored for immune correlative studies.
- Collection of 1 purple top tube for research correlates
- *Only for subjects with sufficient material from an excisional biopsy or, optionally, for patients with circulating lymphoma cells:* Apheresis for collection of peripheral blood

mononuclear cells (PBMC) (approximately 2 hours) to provide adequate sample for immune assays

- *Only for subjects not undergoing apheresis:* 7 additional green top tubes of peripheral blood will be collected for research correlates

4.3 Treatment Period:

The treatment schema and study visit schedule is the same for both the dose de-escalation cohorts and the expanded, phase 2 cohort.

SD-101 will be administered within 12 hours of the completion of radiotherapy during Day 2.

The study agent SD-101 at a dose of either 1 mg or 3 mg will be injected intratumorally on Day 2. Subsequent weekly injections will be administered on days 9, 16, 23 and 30 for a total of 5 intratumoral injections.

Ibrutinib will be taken PO daily starting on Day 10. Dosing will be continuous 560 mg daily throughout the course of the trial. Subjects will continue to take ibrutinib until disease progression or for a total of 96 weeks of therapy, whichever comes first.

All intratumoral SD-101 injections will be carried out at the Clinical Translational Research Unit (CTR) and/or oncology clinic infusion treatment area (ITA). Vital signs, including weight, will be taken prior to each injection. Subjects will be monitored for at least 30 minutes after each injection with repeat vital signs before being discharged home. Vital signs (blood pressure, heart rate, temperature, respiratory rate and oxygen saturation via pulse oximetry) should be obtained at the end of the monitoring period, within a -5/+15 minute window.

All subjects will be evaluated as described below. The first day of treatment is Day 1, which is the first day of Week 1. Subsequent days or weeks listed are with reference to his landmark.

4.3.1 Day 1:

- First treatment of radiotherapy (2 Gy)

4.3.2 Day 2:

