4.3.7 Day 37 (+/- 7 days)

- Obtain vital signs/ ECOG performance status
- Monitoring of concomitant medications
- Assessment of adverse events and toxicity grading according the CTCAE v4.0
- CBC with Differential, and platelet count
- Comprehensive metabolic panel
- Distribution of a 6-week supply of ibrutinib. Ibrutinib will be self-administered by subject daily.
- FNA of accessible tumor, if available, for research studies. If additional sites of disease are safely accessible via fine needle aspiration, these may be biopsied as well.
- Collection of 1 purple top tube for research correlates

- *Only for subjects with sufficient material from an excisional biopsy:* Apheresis for collection of peripheral blood mononuclear cells (PBMC) (approximately 2 hours) to provide adequate sample for research studies (+/- 10 days).
- *Only for subjects not undergoing apheresis:* Collection of 7 additional green top tubes of peripheral blood for research correlates (+/- 10 days).

4.3.8 Weeks 12, 24, 36, 48, 60, 72, 84 (+/- 10 days):

- History and physical examination
- Obtain vital signs/ ECOG performance status
- Monitoring of concomitant medications
- Assessment of adverse events and toxicity grading according the CTCAE v4.0
- Routine CBC, differential, and platelet count
- Routine Comprehensive metabolic panel
- LDH
- Distribution of ibrutinib. Ibrutinib will be self-administered by subject daily.
- Weeks 12, 24, 48, 72 only - Determination of response to treatment with CT scans of the chest/ abdomen/ pelvis or other medically appropriate imaging modality to evaluate all areas of disease followed by calculation of response by the Cheson Criteria (49) for lymphoma subjects (draining lymph nodes of the injected region will be excluded from this assessment, since SD-101 injections may cause transient enlargement of the draining lymph nodes). CT scan is the preferred mode of imaging, however, if a CT scan is contraindicated or if it is felt by the Sponsor Investigator that a PET/CT will be a better modality to assess a particular subject, a PET/CT may be used for evaluation.
- Collection of 1 purple top tube for research correlates
- *Optional:* If there is no evidence of disease on CT scan, a bone marrow biopsy will be obtained to document whether a complete response is achieved.
- At Week 12 only, 7 additional green top tubes of peripheral blood will be collected

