6. DOSE MODIFICATIONS

6.1 Dose/ Schedule Modifications of SD-101

The SD-101 dose of will not be reduced except by the rules listed in the study design. In the case of adverse events affecting the feasibility or safety of injection, as judged by the investigator, injections may be delayed or omitted until resolution of the adverse event to Grade ≤ 1 or baseline and after re-assessment by investigator. When doses are delayed, all five intratumoral injections may still be delivered, provided all five are given within a span of 8 weeks and there is a minimum interval of 3 days between injections. In the case of local injection site reactions that cause dose delays or modifications and are not DLTs, the Investigators are asked to avoid administering subsequent injections near to this site and to document the reaction with a photograph when possible.

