8. CORRELATIVE/SPECIAL STUDIES

8.1 Blood and tissue acquisition

Research blood draws will be processed within the laboratory of [name] at Stanford University and stored as cryopreserved peripheral blood mononuclear cells (green top tubes) and plasma (purple top tubes).

Excisional lymph node biopsy prior to first dosing, which will be processed and stored as single cell suspensions within the laboratory of [name] at Stanford University.

FNA biopsies will be processed within the laboratory of [name] at Stanford University and stored as single cell suspensions.

Leukapheresis to obtain peripheral blood mononuclear cells (PBMC) may be performed during the screening period (prior to Day 1) and at Day 37, if excisional biopsy is obtained at screening.

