8.2 Storage of blood and tissue samples

Samples will be stored as viable single cells suspensions in liquid nitrogen and cell-depleted serum at -80°C within the laboratory of [name] at Stanford University. Remaining unused samples will be stored for potential future correlative studies including flow cytometric studies with additional potential biomarkers, gene expression analysis, and high-throughput sequencing of immunoglobulin and T-cell receptors.

Access to samples will be limited only to research personnel involved in performing the correlative studies. Samples will be labeled with a unique subject identification code and all sample consent, acquisition, handling, storage and processing will be in accordance with

HIPAA and any other state or federal laws or regulations concerning the use or storage of human tissue for research purposes.

8.3 Lymphocyte activity against autologous tumor (performed if adequate tumor sample):

PBL and/or PBMCs will be obtained from all subjects, as described above, cryopreserved, and thawed, then used to for detection of tumor-specific T-cell responses by flow cytometry.

Autologous tumors undergo negative selection with antibody-bound paramagnetic beads and are then activated for 72 hours with CpG. These activated tumor B-cells are irradiated to 50 Gy in a Cesium-137 irradiator then used as stimulator cells in 24 hour co-culture with autologous subject PBMCs collected at the specified time points. Negative controls run in parallel include PBMC incubated with media alone. Positive controls for lymphocyte functional capacity will include anti-CD3 plus anti-CD28 stimulation. After co-culture, PBMC are stained for CD4; CD8; and a panel of T cell activation associated markers. Tumor-specific immune responses are calculated as the increase in percentage of activated T-cell subsets (CD4 or CD8) specifically in response to co-culture with autologous tumor at post-treatment time points compared to pre-treatment time points.

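### The window for the Day 37 primary immune sample overlaps the fifth-injection window, so a nominally post-course sample can be drawn before the last injection

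*Combined protocol and SAP*

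**What the plan says.** Section 1.2 lists induction of tumor-specific immune responses as the second secondary objective, and Section 10.4 describes the measure as exploratory. Section 10.4.4 defines it as a change from pre-treatment to post-treatment time points and adds: "All post-treatment time points will be evaluated, but the primary timepoint for analysis will be from Day 37 samples".

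The assay in Section 8.3 works on blood mononuclear cells, with tumor cells "used as stimulator cells in 24 hour co-culture with autologous subject PBMCs collected at the specified time points". Those cells come from apheresis or from green top tubes; under Section 8.1 research blood is "stored as cryopreserved peripheral blood mononuclear cells (green top tubes) and plasma (purple top tubes".

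Section 4.3.7 and the study calendar give the Day 37 visit 7 days either side, but the two collections that supply the assay have a wider window. For apheresis, the sample is taken "to provide adequate sample for research studies (+/- 10 days". For everyone else the entry is "Collection of 7 additional green top tubes of peripheral blood for research correlates (+/- 10 days".

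On the injections, Section 4.3 puts the first on Day 2 and continues: "Subsequent weekly injections will be administered on days 9, 16, 23 and 30 for a total of 5 intratumoral injections". Section 4.3.6 allows the fifth 2 days either side of Day 30. Section 6.1 lets injections be delayed or omitted for adverse events, and after delays "all five intratumoral injections may still be delivered, provided all five are given within a span of 8 weeks". Study days are counted from Day 1. Nothing in the plan requires the Day 37 sample to follow injection 5, and post-treatment is not defined.

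**The concern.** The nominal dates suggest that Day 37 was placed one week after the end of the injection course. The windows do not protect that interval. The sample's window starts before the fifth injection's window opens and runs on past it, so one primary time point can pool subjects who have had four injections with subjects almost three weeks past their fifth.

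Delays add to this. They follow adverse events that affect injection, so a delayed subject's Day 37 sample falls earlier in the course for a reason connected with how that subject reacted. The endpoint is read in at most the 21 to 24 subjects expected at the recommended phase 2 dose (Section 12.3.2), and in fewer once adequate research samples are required (Section 10.4.1). A few early samples could move the summary, and the plan does not say how to identify or handle them.

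**Working it through.** The plan states no figure to reproduce. The check is calendar arithmetic on its own days and windows.

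**Nominal schedule.** Injection 5: 2 + 4 × 7 = Day 30. Interval to the sample: 37 − 30 = 7 days. The nominal days are consistent with each other.

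**Windows.**
- Assay sample (Section 4.3.7, ±10): 37 − 10 = Day 27 to 37 + 10 = Day 47.
- Injection 5 (Section 4.3.6, ±2): Day 28 to Day 32.

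**On-schedule subjects.**
- Earliest sample against latest injection 5: 27 − 32 = −5, so up to 5 days before it.
- Latest sample against earliest injection 5: 47 − 28 = 19 days after it.
- A Day 27 sample precedes every on-schedule injection 5, since the earliest is Day 28. Against a nominal Day 30 injection, samples on Days 27, 28 and 29 precede it.
- If the ±7 visit window is applied instead (Day 30 to 44), the overlap shrinks but remains: 30 − 32 = −2.

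**Delayed subjects.** With injection 5 on Day 30 + d:

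| Delay d (days) | Injection 5 | Nominal Day 37 sample minus injection 5 | Range over Day 27 to 47 |
|---|---|---|---|
| 0 | Day 30 | +7 | −3 to +17 |
| 7 | Day 37 | 0 | −10 to +10 |
| 14 | Day 44 | −7 | −17 to +3 |
| 21 | Day 51 | −14 | −24 to −4 |
| 28 | Day 58 | −21 | −31 to −11 |

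A sample can follow injection 5 only if 47 > 30 + d, that is d < 17. At d = 17 the latest sample falls on the injection day. At d = 18 injection 5 is on Day 48 and every permitted sample precedes it.

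**The 8-week limit.** Counted from injection 1 on Day 2, as 55 or 56 days, the last injection can fall on Day 57 or 58. The latest permitted sample is then 10 or 11 days too early, and a Day 27 sample is 30 or 31 days too early.

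**Does a later sample already exist?** Green top tubes are collected from all patients at Week 12, ±10 days (Section 4.3.8 and study calendar footnote 13). Taking Week 12 as Day 84, the earliest draw is Day 74. Taking the first day of Week 12, 1 + 11 × 7 = Day 78, the earliest is Day 68. Either is after Day 58.

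**Window after the fix.** With 0/+10 days the sample falls on Day 37 to 47. In on-schedule subjects that is 37 − 32 = 5 to 47 − 28 = 19 days after injection 5.

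**The case against.** The best defence is that the plan never says the endpoint measures a completed injection course. The objective concerns the combination, and ibrutinib continues to Week 96, so no Day 37 sample is after all treatment. Section 10.4.1 admits anyone who has had a single injection at the recommended dose. Green top tubes are also drawn on Days 9 and 16, mid-course, and all post-treatment points are to be evaluated, so the term reads most naturally as after treatment starts. A fixed time from Day 1 is a legitimate choice. This stands, and it is why the calendar anchor should be kept.

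Early sampling is also an edge case. The nominal draw is a week after injection 5, and drawing before it mostly means taking the Day 37 blood ahead of the Day 30 visit. The plan gives no frequency for long delays. Its nearest indication is 2 of 30 subjects with interrupted injections in the cited 18 mg study of a different CpG agent (Section 5.1). That stands too, but it bears on how often the problem would arise, not on whether the window allows it.

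A reader might infer that a weak immune result could never be separated from a timing artefact. The documents do not support that: subjects still on study at Week 12 give a sample after any permitted injection, and it will be evaluated. What is missing is a rule for using it, since Day 37 is primary.

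A reader might also infer that the sample should be timed from the last injection actually given, at no cost. That does not hold either. Injections may be omitted, so 7 days after a sole Day 2 injection is Day 9, before ibrutinib starts on Day 10. After two injections it is Day 16, about 6 days into ibrutinib. For a last injection on Day 58 the draw would fall from Day 65, when no visit is scheduled, so an extra visit would usually be needed.

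**Conclusion.** The concern holds as a defect in a sampling window. The stated windows let the primary immune sample be drawn up to 5 days before injection 5 in an on-schedule subject, or up to 2 days before under the narrower visit window. From a delay of about 18 days, counted from nominal Day 30, no permitted sample can follow injection 5.

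The on-schedule result rests only on the stated days and windows. The Day 57 to 58 limit assumes that the 8 weeks run from injection 1 on Day 2; counting 55 or 56 days gives the same conclusion. How many subjects would be affected cannot be derived from the documents.

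The consequence is modest. The endpoint is exploratory, no hypothesis test or decision rule is attached to the Day 37 value, and the response-rate, progression-free survival and DLT analyses are unaffected. The change is worth making because it is cheap and removes an avoidable source of variation from a small sample.

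**What to change.** 1. Make the Day 37 apheresis and green-top window forward-only, for example 0/+10 days, and require the draw to follow injection 5 in subjects who are on schedule. The visit's own window, safety labs and ibrutinib resupply can stay as they are.
2. Keep the calendar Day 37 draw for subjects with delayed or omitted injections. Do not re-anchor it to the last injection given.
3. Record for every subject the number of injections received and the days from last injection to sample, and state what post-treatment means for this endpoint.
4. Pre-specify a sensitivity analysis that flags Day 37 samples taken on or before the last injection and uses the Week 12 green-top sample as the post-course value for those subjects. Note when reporting it that Week 12 also carries longer ibrutinib exposure and is available only for subjects still on study.

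The cost is a short amendment, a narrower scheduling window and one added analysis. A subject who attends the Day 37 visit early, on Day 30 to 36, would need the research draw on a later day. No new assay time point is needed and the injection schedule is not changed.

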11. REGULATORY CONSIDERATIONS

11.1 Institutional Review of Protocol

The protocol, the proposed informed consent and all forms of participant information related to the study (eg, advertisements used to recruit participants) will be reviewed and approved by the Stanford IRB and Stanford Cancer Institute Scientific Review Committee (SRC). Any changes made to the protocol will be submitted as a modification and will be approved by the IRB prior to implementation. The Protocol Director will disseminate the protocol amendment information to all participating investigators.

11.2 Data and Safety Monitoring Plan

The Stanford Cancer Institute Data and Safety Monitoring Committee (DSMC) will be the monitoring entity for this study. The DSMC will audit study-related activities to determine whether the study has been conducted in accordance with the protocol, local standard operating procedures, FDA regulations, and Good Clinical Practice (GCP). This may include review of the following types of documents participating in the study: regulatory binders, case report forms, eligibility checklists, and source documents. In addition, the DSMC will regularly review serious adverse events and protocol deviations associated with the research to ensure the protection of human subjects. Results of the DSMC audit will be communicated to the IRB and the appropriate regulatory authorities at the time of continuing review, or in an expedited fashion, as needed.

11.3 Data Management Plan

The Protocol Director and Coordinator will prepare and maintain adequate and accurate participant case histories with observations and data pertinent to the study. Case Report Forms (CRFs) are printed to record all protocol-related information on each trial participant. CRFs will summarize the clinical findings and observations necessary to ensure safety of participants on the study. CRF design and creation will be completed prior to enrollment of the first participant. The plan is to work with the OnCore Team [contact] for CRF design and storage as well as in all subject binders that will include same CRFs to be kept locked in the lymphoma research area.

These study-specific Case Report Forms (CRFs) will document treatment outcomes for data analysis. Case report forms will be developed using the above mentioned OnCore database system and will be maintained by the OnCore team, Research Coordinator and Protocol Director. CRFs will be kept in a locked office, only accessible to the research team.

